Title: Effect of health education on promoting influenza vaccination health literacy among primary school students: a cluster randomized controlled trial protocol

NCT number: NCT06048406

Document date: 01 September 2023

INTRODUCTION

The Influenza virus, known for its mutability and potent infectivity, poses a significant health risk. Recent trends indicate an escalating incidence of influenza in China, thereby posing a substantial threat to public health.^{1,2} According to national influenza surveillance data, each October marks the onset of the winter and spring influenza epidemic seasons across various regions in China.^{3,4} Currently, the most effective preventative measure against influenza is vaccination.⁵ Seasonal influenza vaccinations have demonstrated efficacy in reducing the risk of influenza infection and severe complications across all age groups.⁶ Seasonal influenza epidemics often precipitate outbreaks in densely populated areas such as schools, childcare institutions, and nursing homes.⁶

Health literacy, defined as an individual's capacity to acquire, comprehend, and utilize basic health information and services for informed health decisions, plays a pivotal role in vaccination uptake.^{7,8} Enhancing vaccine health literacy can potentially augment vaccination willingness and mitigate vaccination hesitancy.⁹ Therefore, improving the population's awareness, attitudes, and behaviors towards influenza vaccination health literacy is integral to the successful implementation of influenza

prevention and control measures and strategy development.

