The proposed study is a cluster randomized controlled trial. Two administrative districts, one in the central urban area and the other in the non-central urban area of Dongguan, will be selected for this study. Within each district, ten primary schools will be randomly selected, with half designated as intervention group schools and the remaining half as control group schools. This results in a total of twenty primary schools, evenly split between the intervention and control groups.

The intervention group will receive a health education intervention focused on influenza vaccination, while the control group will continue with their routine school health education. The intervention period for this study is projected to last approximately three to four months. Data collection will conduct at the onset and conclusion of the intervention period. The primary outcomes of interest are the differences in influenza vaccination rates and influenza vaccination health literacy levels between the experimental and control groups, which will be used to evaluate

the effectiveness of the intervention. The overview of the study procedure is shown in the Figure 1.

Study sample

Study participants are primary school students in grades 4 to 5 in Dongguan City.

Inclusion criteria include: 1) Primary school students within the age range of 7-12 years. 2) Students and their parents who voluntarily agree to participate in the study and provide signed informed consent. 3) Permanent residents of Dongguan City who are expected to complete the project without transferring schools during the study period.

In addition, individuals with contraindications to influenza vaccination, who have recently received an influenza vaccination, diagnosed with influenza or confirmed as influenza-like cases at the commencement of the study, or unwilling to participate in the project, will be excluded.

Sampling method

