Staff of the affiliated street Center for Disease Prevention and Control (CDC) will visit the school in the first month to implement intervention activities using the health education intervention package. The intervention period will commence in September 2023 and conclude in February 2024, resulting in a total intervention duration of approximately three to four months. The specific intervention process is as follows: 1) At the start of the semester (early intervention stage in September 2023), initiation activities will be conducted. The investigators will introduce the study to teachers and students, and medical professionals or public health experts will be invited to deliver classroom lectures at the intervention group schools. Baseline data will be collected at this stage. 2) During the intervention period (September 2023 – January 2024), the intervention group will follow the health education intervention toolkit to conduct intervention activities. 3) At the conclusion of the semester (February 2024), follow-up data will be collected. The intervention timeline is shown in the Figure 2.

Data collection and analysis

Questionnaire surveys will be administered to students and parents before and after

the intervention, using self-completion. The questionnaire design, which is informed by similar research literature (Appendix 1 & 2), will undergo evaluations for reliability and validity. The questionnaire will include the following content: 1) Socio-demographic characteristics (name, age, sex, class, residential address, parents' educational level, occupation, family income); 2) Personal history (basic disease history, allergy history, and personal history); 3) Influenza vaccination health literacy level. The health literacy level concerning influenza vaccination will be assessed across four dimensions: knowledge, attitude, behavior, and skills related to influenza vaccination. Details of these four dimensions include knowledge of basic facts about the influenza vaccine (such as its efficacy, vaccination frequency, and side effects), attitudes towards the influenza vaccine (including perceptions of its efficacy and safety), behavioral characteristics related to influenza vaccination (such as willingness to be vaccinated, vaccination status, and timing of vaccination), and sources of information about the influenza vaccine.

Confirmation of influenza and surveillance of influenza-like cases

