Influenza cases are characterized by initial symptoms such as fever, headache, myalgia, and general malaise, with body temperatures potentially reaching 39-40°C. Patients may experience chills, muscle and joint pain, fatigue, loss of appetite, nasal congestion, runny nose, substernal discomfort, facial flushing, and conjunctival hyperemia. Confirmed cases must have one or more of the following positive pathogenic test results: influenza virus nucleic acid test, influenza antigen test, influenza virus culture isolation, and a four-fold or greater increase in the level of influenza virus-specific IgG antibody in the convalescent and recovery period double sera compared to the acute stage.

Confirmed cases of influenza will primarily be identified through the municipal CDC influenza surveillance network. Furthermore, influenza-like illness (ILI) is defined as instances of fever (body temperature $\geq 38^{\circ}\text{C}$) accompanied by either a cough or sore throat, with epidemiological evidence or a positive influenza rapid antigen test, and excluding other diseases that cause influenza-like symptoms. The fever should occur within the current acute febrile illness period. Body temperature identification includes self-measurement by patients and temperature detection by medical institutions. Identification of ILI cases can be achieved through establishment of a case reporting system in schools or student or parent self-report. The case reporting system in schools involves training school medical staff and teachers to understand the definition and reporting methods for ILI cases. When students exhibit influenza-like symptoms (such as fever, cough, sore throat, or other symptoms), the school's medical staff or teachers will report these cases. Concurrently, a morning inspection and registration system for illness-related absenteeism will be implemented. Cases identified through the student or parent self-report will be obtained by questionnaires, telephone calls, emails, or online platform reports.

Study outcomes

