Primary outcomes include the influenza vaccination rate and the influenza vaccination health literacy level. The influenza vaccination rate will be calculated as the number of vaccinated individuals divided by the total number of individuals, multiplied by 100%. Regarding the influenza vaccination health literacy level, each correct answer for the scale will be scored as one point, with incorrect answers receiving no points. Based on the scores, health literacy levels will be categorized as low, medium, or

high.

Secondary outcomes include influenza incidence, the ILI incidence and the influenza vaccine protection rate. The influenza incidence will be calculated as the number of individuals diagnosed with influenza divided by the total number of individuals, multiplied by 100%, The ILI incidence will be calculated as the number of ILI cases divided by the total number of participants, multiplied by 100%. The influenza vaccine protection rate will be calculated as the difference between the incidence rate in unvaccinated individuals and the incidence rate in vaccinated individuals, divided by the incidence rate in unvaccinated individuals, multiplied by 100%.

Statistical analysis plan

Continuous variables will be described using means \pm standard deviation or median (interquartile range), and comparisons will be made using two independent samples t-tests or Wilcoxon rank-sum tests. Categorical variables will be described using frequency and composition ratios, and rate comparisons will be conducted using Chi-square tests or Fisher's exact probability method. The association between the level of influenza vaccination health literacy and vaccination willingness will be analyzed using multivariate logistic regression.

Quality control

Quality Control will be conducted in accordance with the requisite quality control standards, with dedicated on-site quality control personnel assigned to oversee investigation and evaluation. These personnel should be proficient in various testing technical requirements and quality control points, and familiar with the on-site

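### The disease outcomes appear to close in February 2024, before the spring part of the season the protocol describes, and the vaccine protection rate makes no allowance for children vaccinated late

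*Combined protocol and SAP*

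**What the plan says.** **Season.** The Introduction states that "each October marks the onset of the winter and spring influenza epidemic seasons across various regions in China". It gives no end month and nothing specific to Dongguan.

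**Collection points.** Study design says "Data collection will conduct at the onset and conclusion of the intervention period". Intervention time places baseline collection in September 2023 and then says "At the conclusion of the semester (February 2024), follow-up data will be collected". No later time point appears.

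**Vaccination during follow-up.** Vaccination services are part of the intervention package (Intervention methods), with no calendar limit. Intervention time says "During the intervention period (September 2023 – January 2024), the intervention group will follow the health education intervention toolkit". Recently vaccinated children are excluded at entry (Study sample), so most vaccinated children in the analysis will have had their dose after the September start.

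**Disease outcomes.** Study outcomes says "Secondary outcomes include influenza incidence, the ILI incidence and the influenza vaccine protection rate". Incidence is cases divided by the number of individuals. The protection rate is the relative difference in incidence between unvaccinated and vaccinated children. No person-time, dose date, lag or observation window is given. Objective 1 includes the rate of influenza infection, and Objective 3 is vaccine efficacy.

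**Case source.** The section on confirmation and surveillance says "Confirmed cases of influenza will primarily be identified through the municipal CDC influenza surveillance network". It adds school and self-reporting for influenza-like illness (ILI). No start or end date is given for any of these.

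**The concern.** A February close suits vaccination uptake and health literacy, which are the targets of the education programme. Disease outcomes depend on when influenza circulates and on how long vaccinated children are observed after their dose. If case counting also ends in February, the spring part of the season is not counted, and children vaccinated in December or January contribute little protected time.

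Two things are at stake. A part-season incidence could be reported as the season's incidence. The protection rate, on which Objective 3 wholly depends, would rest on fewer events and would be pulled towards zero, because time before the dose counts as vaccinated time.

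**Working it through.** The plan gives no figure for the length of the season or of the disease follow-up, so there is none to reproduce. The sample size (138 × 20 = 2760; 2760 × 1.10 = 3036) is built on the vaccination rate and does not bear on this point.

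**1. Share of season days covered.** Start: 1 October 2023 (month from the Introduction, first day assumed). Close: 1 to 29 February 2024, which gives 124 to 152 days counted inclusively. Season end: assumed.

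| Assumed season end | Season days | Covered | Unobserved |
|---|---|---|---|
| 31 March | 183 | 124/183 to 152/183 = 68-83% | 17-32% |
| 30 April | 213 | 124/213 to 152/213 = 58-71% | 29-42% |
| 31 May | 244 | 124/244 to 152/244 = 51-62% | 38-49% |

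These are shares of days, not of cases. The documents give no epidemic curve.

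**2. Follow-up after the dose**, from dose date to 1 or 29 February:

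- 1 November: 92-120 days
- 1 December: 62-90 days
- 1 January: 31-59 days (17-45 after an assumed 14-day lag)
- 31 January: 1-29 days (at most 15 after that lag)

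**3. Dilution of the protection rate.** Assume constant risk from 1 October, a 14-day lag, and doses spread evenly over the 123 days from October to January. Mean protected time is T − 14 − 61.5 days. When risk is low, apparent protection is roughly true protection × (protected days / T).

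- Close on 29 February (T = 152): 76.5/152 = 0.503. True 60% appears as about 0.60 × 0.503 = 30%.
- Close on 30 April (T = 213): 137.5/213 = 0.646. True 60% appears as about 0.60 × 0.646 = 39%.

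The full cumulative-incidence calculation, with 5-20% of unvaccinated children infected by 29 February, gives 28-30% and 35-38%. For true protection of 40% it gives 19-20% and 23-25%. If all doses fall within the first 61 days, true 60% appears as 40-42% and 44-47%. A later close reduces the dilution but does not remove it.

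**4. Precision.** Assume 2760 children, 65% vaccinated (midway between the planned 80% and 50%), 5% full-season incidence in the unvaccinated, true protection 50%, and no clustering. Expected events are 966 × 0.05 = 48 unvaccinated and 1794 × 0.025 = 45 vaccinated. SE(log RR) = √(1/48.3 + 1/44.85) = 0.207, so the 95% interval for protection is about 25-67%. With 80% of events it is 21-68%, and with 60% it is 16-70%. Clustering would widen all three. This calculation holds protection at 50% and does not include the dilution in step 3.

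**5. The period itself.** Intervention time says "The intervention period will commence in September 2023 and conclude in February 2024" and continues "resulting in a total intervention duration of approximately three to four months". The shortest reading, 30 September to 1 February, is 124 days; the longest, 1 September to 29 February, is 181 days. The activity window is given separately as ending in January. Collection is tied to the conclusion of this period, so these statements must be reconciled.

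**The case against.** **The February stop for cases is inferred.** This stands. The Intervention time section does not say that case surveillance ends in February, and the surveillance section has no stop date. Figures 1 and 2 were not available for this check, so a window drawn there cannot be excluded. A reader might infer that the protocol rules out observing spring; the text does not go that far. It names two collection points and nothing later. If surveillance is meant to continue, the window for three outcomes is still undefined.

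**The missed share may be much smaller than half.** This stands. A reader might settle on 38-49%, but that requires a season lasting to 31 May. The supportable range is 17-49%.

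**Vaccination may happen early.** This partly stands. Staff visits fall in the first month and lectures in September, which points to earlier uptake. A reader might infer that vaccinated children are observed mostly before or just after the dose. With doses spread evenly from 15 September to 31 January, a close on 15 February and a 14-day lag, that is 69 + 14 = 83 of 153 days (54%). This is barely more than half and rests on assumed dosing dates, so it should not be stated as a finding.

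**Longer follow-up does not cure the dilution.** Correct, as step 3 shows; the formula must change as well.

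**Only secondary outcomes are touched, and a September-to-February incidence is a legitimate quantity.** Both are true. Neither objective promises a full-season figure, but the plan does not label its figure as part-season either.

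**Conclusion.** The concern holds in limited form. As written, the disease outcomes appear to close in February 2024, while the protocol describes a season that includes spring. About 17-49% of season days would go unobserved, depending on the February date and on an assumed season end between 31 March and 31 May. Late-vaccinated children add little follow-up after the dose, and the formula turns this into an understated protection rate. In the illustration with doses spread from October to January, true protection of 60% appears as 28-30% at 29 February. That size rests on assumed dosing dates, lag and constant risk; the direction follows from counting pre-dose time as vaccinated time.

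Influenza incidence, ILI incidence, the protection rate and Objectives 1 and 3 are affected. The comparison of uptake and literacy between arms is not. The change is worth making because Objective 3 has no other support, but it does not threaten the trial's primary result.

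**What to change.** 1. Keep February 2024 for the vaccination rate and health literacy.
2. State the start and end of observation for each disease outcome, and reconcile the statements on the length of the intervention period.
3. For confirmed influenza and the protection rate, extend observation to a prespecified end-of-spring date through one later request to the municipal CDC network for the enrolled children. This depends on consent and on the network being able to return child-level results, which the protocol does not establish. Report both the to-February and the extended result.
4. Compute the protection rate with vaccination as a time-varying status, person-time at risk and a prespecified lag.
5. Settle vaccination status after February. The questionnaires are the only source the documents describe. Either request later vaccination dates from the same network, or state that status is fixed at February and report this as a limitation. The printed items ask about doses in 2023, so the follow-up version should also cover early 2024.
6. If the later request is not possible, label the outcomes September 2023 to February 2024 and limit Objectives 1 and 3 to that period. ILI can stay at February under that label in either case, which spares the schools extra work.

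**Cost.** A few sentences in the protocol, one data request and a somewhat fuller analysis. Secondary disease results would arrive about three to four months later, some children may move away, and doses after February may be misclassified if their dates are not obtained. Primary outcomes and the number of questionnaire rounds do not change.

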Do you think the flu vaccine needs to be given every year to

prevent the flu?

Do you think getting a flu vaccine is good for you and your child's health?

Do you think it is necessary to get a flu vaccine?

Are you confident that the flu vaccine is safe?

Behavioral questions

Within the last year, have you ever had influenza (or had a sudden onset of illness with a high fever $\geq 38^{\circ}\text{C}$ accompanied by flu-like symptoms such as generalised malaise, myalgia, sore throat, etc.)?

If yes, when was the last time you had influenza (or had a sudden onset of illness with high fever $\geq 38^{\circ}\text{C}$ accompanied by influenza-like symptoms such as generalised malaise, myalgia, sore throat, etc.)?

Has your child had influenza (or had a sudden onset of illness with high fever $\geq 38^{\circ}\text{C}$, accompanied by flu-like symptoms such as generalised weakness, myalgia, sore throat, etc.) within the last year?

If yes, when was the last time your child had influenza (or had a sudden onset of illness with a high fever $\geq 38^{\circ}\text{C}$ accompanied by influenza-like symptoms such as generalised malaise, myalgia and sore throat)?

Have you taken your child for a flu vaccination between 2020 and 2022?

Have you or your spouse been vaccinated against flu in 2023?

If you have been vaccinated against flu, when did you or your spouse get the flu vaccine this year?

Has your child been vaccinated against flu in 2023?

If your child has been vaccinated against flu, when did your

child get the flu vaccine this year?

If your child has been vaccinated against flu, why did you decide to take your child for a flu vaccination this year?

If your child hasn't been vaccinated against flu, why did you decide not to take your child for a flu vaccination this year?

If your child has not had a flu vaccination this year, are you currently willing to take your child to get one?

Would you be willing to take your child for a flu vaccination in the future?

Would you like to recommend that others get the flu vaccine?

Skill Questions

Do you know how to schedule your flu vaccine?

Do you take an active interest in information about flu vaccinations?

Where do you get information about flu vaccinations?

Appendix II Questionnaire for Health Literacy Study of Influenza Vaccination among Primary School Students in Dongguan City (Student Version)

Question

Basic information

Your class?

Your gender?

How old are you?

knowledge questions

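### If willingness items earn points, and the score and willingness come from the same form, the literacy–willingness regression is partly circular

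*Combined protocol and SAP*

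**What the plan says.** Under Data collection and analysis: "The health literacy level concerning influenza vaccination will be assessed across four dimensions: knowledge, attitude, behavior, and skills related to influenza vaccination". The behaviour dimension is then described as "behavioral characteristics related to influenza vaccination (such as willingness to be vaccinated, vaccination status, and timing of vaccination". The same section says "Questionnaire surveys will be administered to students and parents before and after" the intervention, so there are two respondents, and says that the questionnaire "will undergo evaluations for reliability and validity".

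Under Study outcomes: "Primary outcomes include the influenza vaccination rate and the influenza vaccination health literacy level". For the literacy score, "each correct answer for the scale will be scored as one point", and the score is then grouped as low, medium or high. No item, dimension or form is excluded, and no answer key or cut-points are given.

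Under Statistical analysis plan: "The association between the level of influenza vaccination health literacy and vaccination willingness will be analyzed using multivariate logistic regression". Neither the willingness item nor the respondent is named.

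In Appendices I and II the willingness items stand under Behavioral questions. The parent form has two. One concerns the future and carries no condition. The other asks "are you currently willing to take your child to get one", but only where the child has not been vaccinated this year. The student form has one, without a condition. Each form also asks under the same heading whether the child was vaccinated in 2023.

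**The concern.** Read together, these sections make willingness both a component of the literacy level and the variable to which that level is related. Someone who says they are willing gains a point, is therefore more likely to be rated high, and is then counted as evidence that high literacy goes with willingness. The odds ratio would exceed 1 even if nothing else on the scale had any bearing on willingness, and a real association would be overstated. A reader of the results could not separate the two.

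This is the only association analysis that the Statistical analysis plan names, and it bears on the Introduction's premise that better vaccine literacy may raise willingness.

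A lesser consequence concerns the two primary outcomes. If vaccination status earns a point, part of any literacy difference between arms is uptake, which the package promotes directly through its vaccination service.

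**Working it through.** The plan gives no figure for this analysis, so there is none to reproduce. The size is illustrated under stated assumptions.

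**Inputs from the documents.** Items counted by heading in the appendices:
- student: 7 knowledge + 2 attitude + 5 behaviour + 2 skill = 16
- parent: 10 + 15 + 14 + 3 = 42

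Expected vaccination rates, from Sampling method: 80% versus 50%.

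**Assumptions, not in the documents.** One willingness item is scored; 60% are willing; other items are 60% correct; inter-item correlation r is 0.1 to 0.2; low and high are cut at the scores nearest to thirds; there is no true link (true odds ratio 1).

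**Model.** Score S = X + W. W is the willingness point, Bernoulli(0.6). X is the sum of the other k items, beta-binomial with mean 0.6 and correlation r, independent of W. With low meaning S ≤ l and high meaning S ≥ h,

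OR = [P(X ≥ h−1) / P(X ≥ h)] ÷ [P(X ≤ l−1) / P(X ≤ l)].

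**Example: student form, k = 15, r = 0.1.** The cuts are l = 8 and h = 12. The willing share is 52.2% in the low group and 69.7% in the high group. The odds are 0.522/0.478 = 1.09 and 0.697/0.303 = 2.30, so OR = 2.30/1.09 = 2.11.

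**Spurious high-versus-low odds ratio, best cut (range over tie rules):**

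| Scored set | r = 0.1 | r = 0.2 |
|---|---|---|
| Student, all 16 items | 2.11 (1.89–2.25) | 1.70 (1.64–1.87) |
| Parent, all 42 items | 1.33 (1.33–1.37) | 1.23 (1.23–1.25) |
| Student, 11 items | 2.61 (2.33–3.37) | 2.32 (1.96–2.52) |
| Parent, 27 items | 1.54 (1.54–1.66) | 1.37 (1.35–1.41) |

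The shorter sets are knowledge, attitude, one status and one willingness item: 7 + 2 + 1 + 1 = 11 and 10 + 15 + 1 + 1 = 27. With the willingness item left out, the odds ratio is 1.0.

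**Sensitivity (full sets, best cut).** Varying the share correct over 40–80% and the share willing over 50–80% gives 1.89–3.38 (student) and 1.33–1.46 (parent) at r = 0.1, and 1.60–2.25 and 1.21–1.38 at r = 0.2. With independent items in the base case, the values are 3.40 and 2.05.

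**If there is a real link.** Let willingness correlate 0.1 with every other item. Including it turns 3.3 into 7.4 (student) or 4.0 into 5.1 (parent).

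**Vaccination status in the arm comparison.** One scored status item adds 0.80 − 0.50 = 0.30 points. Within-arm SDs at r = 0.1 and 0.2 are 2.97 and 3.73 (student), 7.03 and 9.42 (parent):
- student: 0.30/2.97 = 0.10 SD, 0.30/3.73 = 0.08 SD
- parent: 0.30/7.03 = 0.04 SD, 0.30/9.42 = 0.03 SD

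On the parent form, a vaccinated child earns the status point but the current-willingness item does not apply. If both are scored and 60% of unvaccinated families are willing, the pair yields 0.80 + 0.20 × 0.60 = 0.92 versus 0.50 + 0.50 × 0.60 = 0.80, a difference of 0.12. At 80% willing it is 0.96 − 0.90 = 0.06; at 30% it is 0.86 − 0.65 = 0.21.

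With 10 schools per arm, 138 students per school and an assumed intracluster correlation of 0.05, power to detect the 0.30-point shift alone is 0.11 to 0.15 (student) or 0.06 to 0.07 (parent).

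**The case against.** The strongest reply is that the scoring rule gives points for correct answers, and a question about willingness has no correct answer. The same is true of the items on dates, reasons and information sources. On that reading only factually keyed items score, and no overlap exists. A second reply is that two forms are used: if one supplies the score and the other the willingness variable, no item is shared. Both replies stand as possibilities, so the point must remain conditional. Neither settles it. The plan adopts neither reading, and scoring only factual items fits poorly with a definition that counts behaviour as a dimension and names willingness within it.

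The full 16- and 42-item sets are also generous to the scale, because they give a right-or-wrong point to items that hardly have one. That is fair, and it is why the shorter sets are shown. They make the artefact larger.

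A reader might infer that the parent form doubles the overlap because it has two willingness items. The documents do not support this for all parents: the current-willingness item is asked only where the child is unvaccinated, so a double overlap is possible only for those parents.

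Finally, the association is not among the three study objectives or the listed outcomes, and behaviour belongs to literacy by the plan's own definition. Both points are correct and limit how serious this is.

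**Conclusion.** The concern holds conditionally. If willingness earns a point and both variables come from the same form, the regression is partly circular. Under the stated assumptions, overlap alone gives a high-versus-low odds ratio of about 1.6 to 2.3 (student) or 1.2 to 1.4 (parent) with all items scored, and about 2.0 to 3.4 or 1.35 to 1.66 with the shorter sets. These figures depend on assumed answer rates, correlations and cuts, and illustrate size rather than predict it. If either condition fails, there is no built-in association.

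A reader might infer that the plan is certainly circular, or that the primary comparison is compromised. The documents support neither. The scored items and the respondent are left open, the vaccination-rate outcome is untouched, and the regression is not the randomised comparison. Status, if scored, does count in both primary outcomes, but adds at most 0.30 points, or about 0.12 on the parent form under the condition shown. Severity is minor to moderate.

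**What to change.** In the Statistical analysis plan, state that the willingness regression uses a literacy score without the willingness item(s) of the form used, and name the willingness item and the respondent, parent or student. This removes the overlap whichever scoring rule applies. Add a sensitivity analysis that repeats the between-arm literacy comparison with the status and willingness items left out, so that a literacy gain can be told apart from uptake.

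Removing the whole behaviour dimension is not needed. At r = 0.1, alpha = nr/[1 + (n−1)r] would then fall from 0.64 to 0.55 (student, 16 to 11 items) or from 0.82 to 0.76 (parent, 42 to 28 items). Dropping only the willingness items leaves 1.5/2.4 = 0.63 (student, 15 items) or 4.0/4.9 = 0.82 (parent, 40 items).

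The cost is a little more analysis and a slightly shorter regression score. The primary outcome definition, data collection and sample size do not change. The choice should be fixed before follow-up data are analysed.
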